Appendix B. Treatment Emergent Adverse Event Algorithm

Dates	eCRF Flag of “Did event start before first dose of investigational product?”	Treatment Emergent?
AE onset date > 1st IP date	No	Yes
AE onset date < 1st IP date	Yes	No
AE onset date > 1st IP date	Yes	Yes
AE onset date < 1st IP date	No	Yes
AE onset date = 1st IP date	No	Yes
AE onset date = 1st IP date	Yes	No
Cannot determine even after date imputation specified in section 9.3.2	Yes	No
Cannot determine even after date imputation specified in section 9.3.2	No	Yes

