6.2.1.1 Dosage, Administration, and Schedule

Eligible outpatient subjects will be randomized and will initiate administration of IP (omeamtiv mecarbil or placebo). Day 1 is defined as the calendar day when treatment with IP is initiated. The first administration of IP should be on the day of randomization but not later than 5 calendar days after randomization. The time when ingestion of the first dose of IP is completed is defined as Time = 0 hours. Baseline procedures must be completed before initiation of IP and can be performed on the same day.

IP will be administered orally BID in the morning and evening by the subjects and can be taken under fasted or fed conditions. IP will be swallowed whole (not chewed) and taken with water as instructed in the IPIM. Administration of each morning and evening dose is to be taken at approximately the same time of day (12 ± 3 hours from the most recent previous dose). If IP cannot be taken or has not been taken within this window, the dose should be recorded as missed and the next dose should be taken at the regular time.

Administration of IP will start with the morning dose on day 1 and will end with the morning dose on the day of the subject's week 16 visit. The quantity, date and time, lot number, and bottle number of investigational product is to be recorded on each subject's eCRF.

6.2.1.2 Rules for Withholding Investigational Product due to Myocardial Ischemia or Infarction, Abnormal Blood Pressure or Heart Rate

Omecamtiv mecarbil may result in signs and symptoms of myocardial ischemia or infarction, as described in Section 7.1 of the Investigator's Brochure (eg, increases in HR, dizziness, dyspnea, hypotension, chest discomfort or pain, ST-segment depression on ECG, and/or elevations in troponin I or T). If a subject reports clinical signs or symptoms suggestive of myocardial ischemia or infarction, and/or experiences changes in BP or HR, withholding of IP should be considered. No antidote to omecamtiv mecarbil exists. Standard medical therapies should be used in the presence of signs or symptoms of myocardial ischemia.

The following are mandatory rules for withholding IP:

- The subject experiences clinical signs or symptoms, including ECG changes, consistent with myocardial ischemia or infarction as determined by the investigator
- The subject experiences a symptomatic decrease in systolic BP on 2 successive measurements

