9. SAFETY DATA COLLECTION, RECORDING, AND REPORTING

9.1 Adverse Events

9.1.1 Definition of Adverse Events

An adverse event is defined as any untoward medical occurrence in a clinical trial subject. The event does not necessarily have a causal relationship with study treatment.

The investigator is responsible for ensuring that any adverse events observed by the investigator or reported by the subject are recorded in the subject's medical record.

The definition of adverse events includes worsening of a pre-existing medical condition. Worsening indicates that the pre-existing medical condition or underlying disease

(eg, diabetes, migraine headaches, gout) has increased in severity, frequency, and/or duration more than would be expected, and/or has an association with a significantly worse outcome than expected. A pre-existing condition that has not worsened more than anticipated (ie, more than usual fluctuation of disease) during the study or involves an intervention such as elective cosmetic surgery or a medical procedure while on study, is not considered an adverse event.

The investigator's clinical judgment is used to determine whether a subject is to be removed from treatment due to an adverse event. In the event a subject, or subject's legally acceptable representative requests to withdraw from protocol-required therapies or the study due to an adverse event, refer to [Section 8.1](#) for additional instructions on the procedures recommended for safe withdrawal from protocol-required therapies or the study.

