9.2 Reporting of Adverse Events

9.2.1 Reporting Procedures for Adverse Events That do not Meet Serious Criteria

The investigator is responsible for ensuring that all adverse events observed by the investigator or reported by the subject that occur after randomization through the Safety

Approved

Follow-up Visit/End of Study (EOS) are reported using the applicable case report form (eg, Event eCRF), including events that are reported to the CEC for adjudication.

The investigator must assign the following adverse event attributes:

- Adverse event diagnosis or syndrome(s), if known (if not known, signs or symptoms)
- Dates of onset and resolution (if resolved)
- Severity [and/or toxicity per protocol]
- Assessment of relatedness to investigational product
- Action taken

The adverse event grading scale used will be the Common Terminology Criteria for Adverse Events (CTCAE) grading scale. The grading scale used in this study is described in [Appendix A](#). If the severity of an adverse event changes from the date of onset to the date of resolution, record a single event for each level of severity on the Event eCRF.

The investigator must assess whether the adverse event is possibly related to IP (omecamtiv mecarbil or placebo). This relationship is indicated by a “yes” or “no” response to the question: “Is there a reasonable possibility that the event may have been caused by IP (omecamtiv mecarbil or placebo)?”

The investigator must assess whether the adverse event is possibly related to any study-mandated activity (eg, administration of investigational product, protocol-required therapies, and/or procedure (including an screening procedure(s)). This relationship is indicated by a “yes” or “no” response to the question: “Is there a reasonable possibility that the event may have been caused by a study activity (eg. administration of investigational product, protocol-required therapies, and/or procedure?)”

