9.2.2 Reporting Procedures for Serious Adverse Events

The investigator is responsible for ensuring that all serious adverse events observed by the investigator or reported by the subject that occur after signing of the informed consent until 30 days after the last dose of IP or Safety Follow-up Visit/End of Study, whichever is later, are recorded in the subject's medical record and are submitted to Amgen. All serious adverse events must be submitted to Amgen within 24 hours following the investigator's knowledge of the event via the applicable eCRF.

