10.8.1 Adverse Events

The Medical Dictionary for Regulatory Activities (MedDRA), using the current version at the time of final database lock, will be used to code all adverse events (AEs) to a system organ class and a preferred term. All adverse event tables will be summarized by actual treatment group. Treatment-emergent adverse events are events with an onset after the administration of the first dose of investigational product through the end of study as defined in [Section 6.3](#).

The subject incidence of AEs will be summarized for all treatment-emergent AEs (TEAEs), serious AEs, AEs leading to withdrawal of investigational product, fatal AEs, and AEs of interest (EOI).

Subject incidence of all treatment-emergent AEs, serious AEs, AEs leading to withdrawal of investigational product, and fatal AEs will be tabulated by system organ class and preferred term in descending order of frequency.

Summaries of treatment-emergent and serious AEs by preferred term in any treatment arm will be provided in descending order of frequency.

Subject incidence of EOIs (structured MedDRA queries and/or customized queries) will be summarized according to the EOI search strategy categories.

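### If severity-split AE records are dated at the change, SAP Appendix B counts a pre-dose event that improves after the first dosing date as treatment-emergent

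*SAP*

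**What the plan says.** **Recording.** Under Protocol 9.2.1, when an event's severity changes the site is to "record a single event for each level of severity on the Event eCRF". Onset date, resolution date and severity are among the attributes the investigator assigns. The section does not say which onset date, or which answer to the pre-dose flag, a severity-level record takes. Protocol 9.1.1 adds: "The definition of adverse events includes worsening of a pre-existing medical condition".

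**Pre-dose events are in the database.** Serious events are collected if they are ones "that occur after signing of the informed consent until 30 days after the last dose of IP" or until the end-of-study visit if that is later (Protocol 9.2.2). Other events are collected from randomization (Protocol 9.2.1 and the notes to Table 2). The first dose should fall on the day of randomization, "but not later than 5 calendar days after randomization" (Protocol 6.2.1.1).

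**Classification.** SAP 6.4 calls an event treatment-emergent if its onset date is later than the first-dose date or the flag is answered no. SAP 10.8.1 puts it this way: "Treatment-emergent adverse events are events with an onset after the administration of the first dose of investigational product". Appendix B lists the outcomes by date and flag. Two rows matter here. Row 3 is "AE onset date > 1st IP date Yes Yes" and row 6 is "AE onset date = 1st IP date Yes No". No row uses severity, and nothing links the records that belong to one event.

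**The concern.** Once an event has been split by severity, its later part reaches the algorithm as a record with its own start date. A rule that sees only date and flag cannot tell a new event from the tail of an old one, or an improvement from a worsening. An event that began before study drug and is resolving on it can then appear as treatment-emergent.

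Safety and tolerability is one of the two primary objectives, and subject incidence of adverse events is the first safety endpoint listed. The trial is descriptive with about 20 subjects per arm, so readers will take individual preferred-term rows at face value.

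**Working it through.** The documents state no figure on this point, so there is none to reproduce. The check is to run the stated rule.

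**Step 1. Is row 3 deliberate?** Compare Appendix B with the SAP 6.4 text (treatment-emergent if onset is after the first-dose date, or the flag is No).

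| Onset vs first-dose date | Flag | Appendix B | SAP 6.4 text |
|---|---|---|---|
| before | Yes | No | No |
| before | No | Yes | Yes |
| same day | Yes | No | No |
| same day | No | Yes | Yes |
| after | Yes | Yes | Yes |
| after | No | Yes | Yes |

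All six cells agree, so the table is the intended rule and not a typing slip.

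**Step 2. Pre-dose event with a severity change, new record dated at the change.** The comparator counts a continuation record only if its grade exceeds the last pre-dose grade.

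| Change | Flag | Appendix B | Grade comparison |
|---|---|---|---|
| improves after Day 1 | Yes | Yes (row 3) | No |
| improves after Day 1 | No | Yes (row 1) | No |
| worsens after Day 1 | Yes | Yes (row 3) | Yes |
| improves on Day 1 | Yes | No (row 6) | No |
| improves on Day 1 | No | Yes (row 5) | No |
| worsens on Day 1 after the dose | Yes | No (row 6) | Yes |
| worsens on Day 1 after the dose | No | Yes (row 5) | Yes |

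An improvement after Day 1 is misclassified under either flag. The Day 1 worsening is missed only with flag Yes. SAP 9.3.2 slightly widens that second case: a start date with the day missing, in the same month as Day 1, is set to Day 1, so a later worsening with flag Yes would also fall in row 6.

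**Step 3. The other dating convention.** If each severity record kept the pre-dose onset date with flag Yes, row 2 would apply. The improvement error would disappear, but every post-dose worsening would be classed No.

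**Step 4. Size.** One subject in an arm of 20 is 1/20 = 5 percentage points. The number of subjects can only be illustrated, because the documents give no event rates for this population. Assume a constant daily rate h = −ln(1 − p)/140 and a chance 1 − exp(−h·d) of an event in d days.

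- Serious events, p = 22% (assumed): h = 0.00177 per day. For d = 10 to 30 days of screening the chance is 1.8% to 5.2%, or 1.4 to 4.2 of 80 subjects.
- All events, p = 60% (assumed): h = 0.00654 per day. For d = 0 to 5 days between randomization and first dose the chance is 0% to 3.2%, or 0 to 2.6 of 80.
- Share changing grade after first dose, 10% to 50% (assumed): low end 1.4 × 0.1 = 0.14; high end (4.2 + 2.6) × 0.5 = 3.4.

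That is roughly 0.1 to 3 subjects in the whole trial, and the high end is generous. It counts subjects whose screening event would stop randomization, has all 80 subjects wait five days, counts post-randomization serious events twice, and includes worsenings after Day 1, which the rule classifies correctly. The two incidence rates resemble those that Protocol section 2.2 reports for an acute heart failure trial, whereas this trial enrols stable outpatients.

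**The case against.** Four points can fairly be made for the plan.

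- **The convention is not visible.** The protocol does not say how a severity record is dated, and eCRF completion instructions lie outside these documents. This stands as a condition on the finding. It does not rescue the rule, because step 3 shows that the other convention loses every post-dose worsening.
- **The default is conservative and even-handed.** Rows 3 and 4 resolve every disagreement between date and flag to Yes. The rule is applied alike in all arms, placebo included, and no hypothesis is tested. This stands against any claim of systematic bias between arms. It does not make a resolving pre-treatment event treatment-emergent.
- **The Day 1 miss needs a mixed record.** The date must follow the severity change while the flag follows the underlying event. Since worsening is itself an adverse event under Protocol 9.1.1, a site may well answer No, and row 5 then captures it. Row 6 also has a natural use: an event that starts on Day 1 before the dose. This stands, so the miss is only possible.
- **A grade test triggered by the flag alone would do harm.** It would drop a new post-dose event mis-flagged Yes. It would also drop a worsening of a non-serious condition that began in screening and so has no recorded pre-dose grade. This stands and limits the fix.

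A reader might go further and infer that the algorithm is wrong in both directions, or that Appendix B contradicts SAP 10.8.1. The documents support neither. The first treats the conditional Day 1 case as certain. The second requires onset in 10.8.1 to mean the first onset of the condition and not the onset of the recorded event, which the SAP does not say.

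**Conclusion.** The point holds in a limited form. Given separate records per severity level, and records dated at the change, the stated rule counts a pre-dose event that improves after the first dosing date as treatment-emergent, whichever way the flag is answered. That is a wrong result from a stated rule, not merely missing detail. The missed Day 1 worsening is a possibility that depends on how sites answer the flag.

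Few subjects are likely to be affected and there may be none. The 0.1 to 3 range rests wholly on assumed rates. The effect on a single row is not negligible, at 5 percentage points per subject in an arm of 20, provided the subject has no other treatment-emergent event under that term. This should be corrected before database lock, but it does not threaten the trial's overall conclusions.

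**What to change.** In SAP 6.4 and Appendix B:

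1. State that a severity-split record takes the date of the severity change as its onset.
2. Link the records of one event: same preferred term, and a start date contiguous with a recorded pre-dose record.
3. For a linked continuation record starting on or after the first dosing date, set treatment-emergent to No if its grade is not higher than the last recorded pre-dose grade, and to Yes if it is higher. This includes post-dose Day 1 records with flag Yes.
4. Leave every record with no linked pre-dose record, or with no recorded pre-dose grade, under the present Appendix B rows. Flag Yes alone then never removes an event whose onset is after the first dosing date.

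The cost is a few sentences and a small derivation from grade, dates and flag, all of which are already planned for collection. No protocol change is needed. The downside is that split records must be linked in programming. Protocol 9.2.1 lists onset dates but not times, so the SAP should also say how a Day 1 change is judged to have followed the dose.
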